6.5. Risk minimization

In this study, when there are bugs in the software, doctors can still operate under their own judgment without affecting conventional diagnostic and treatment measures, greatly reducing the risk of the test.

6.6. Related benefits

Subjects will be randomly assigned to an experimental group or a control group. And experimental subjects may increase the detection of polyps and other lesions.

6.7. Overall feasibility analysis

EndoAngel is an independent system including both software and computer hardware, which can monitor image data 24 hours a day. The system is not invasive. The overall operability is strong.

7. Statistical Analysis

7.1. Statistical Analysis Plan

Data management and statistical analysis were implemented by Renmin Hospital Wuhan University.

7.2. Methods

Continuous variables should be described by number of subjects, mean, standard deviation, median, minimum and maximum. The classification variables are summarized by frequency and percentage.

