Expected effect:	ENDOANGEL's intended use is to assist doctors in identifying patients who require a second colonoscopy, thus avoiding missed adenomas and excessive washing time costs due to subjective factors and poor decision-making. It can improve the quality of endoscopy and the detection rate of digestive tract lesions.
Primary Endpoint:	1. Adenoma detection rate (ADR); 2. Boston Bowel Preparation Score of intestinal segment in artificial intelligence system;
Secondary Endpoints:	1. Polyp detection rate (PDR); 2. Mean number of adenomas per procedure (MAP); 3. Mean number of polyps per procedure (MNP); 4. The detection rate of large, small and micro - small adenoma and the average number of detection; 5. The detection rate and average number of polyps in large, small and micro-sized polyps; 6. Adenoma detection rate (ADR) of different location 7. Mean number of adenomas per procedure (MAP) of different location 8. Scope-forward time; 9. withdrawal time; 10. Cecal intubation rate; 11. Boston Bowel Preparation Score of endoscopists;
Trail design:	prospective, single group, observational, single-centre
Participants:	Male and female subjects aged 18 years or older will require a colonoscopy, and voluntarily provide endoscopic imaging data and sign an informed consent form.
Sample size:	200 samples were collected to explore the sample distribution, and then calculate the sample size according to the sample distribution.
Study Process:	Subjects who met all inclusion criteria and did not meet all exclusion criteria were included in the study before colonoscopy. During the colonoscopy, the endoscopists need to remain in the same without withdrawal while flushing the bowel. The biopsied patients are followed up for one week. the non-biopsied patients are followed up at the end of their colonoscopy , and the results are sent to an independent data analysis team for review. We will collect the patients' video and exclude the clips of irrigation, biopsy, and

[figure not shown]

	observation of polyp. Then the EndoAngel evaluates the Boston Bowel Preparation Scale of the ascending colon, transverse colon and descending colon, and calculates the proportion of 1 Score.
Security	Safety incidents shall be evaluated and reported according to the quality management measures for clinical trials of medical devices

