Deep learning is an important breakthrough in the field of artificial intelligence in the past decade. It has great potential in extracting tiny features in image analysis and image classification. In 2017, the journal Nature published a paper showing that using artificial intelligence to diagnose skin diseases can reach the level of experts¹¹. Subsequently, in the field of digestive endoscopy, more and more studies began to apply artificial intelligence to assist doctors to find polyps and improve the detection rate of polyps and adenomas.Urban, G. team used artificial intelligence to identify polyps with 95% sensitivity¹². Misawa, M team used artificial intelligence to identify polyps with 90% sensitivity¹³. The purpose of our research group is to develop the EndoAngel with real-time intestinal cleanliness assessment. It can derive a decision curve for bowel cleanliness based on the relationship between the percentage of bowel segments with a Boston score of 1 and the detection rate of missed adenomas. It can help endoscopists to identify patients who need a second colonoscopy, to avoid the detection of missed adenomas and the high cost of cleaning time caused by the wrong decision-making. At the same time, artificial intelligence is in

the preliminary research stage in the field of digestive endoscopy, our research results are expected to provide new ideas in improving the detection rate of colonoscopic adenomas.

2. Patient Selection

Male and female subjects aged 18 years or older will require colonoscopy. And they voluntarily provide endoscopic imaging data and sign informed consent form.

Patients not meeting the inclusion criteria or meeting exclusion criteria will not be considered for participation in the study. Patients who met all criteria and signed informed consent may be excluded from the study due to:

- Endoscopists' professional advices/medical reasons (only under very limited conditions to avoid researcher bias).
- Withdraw informed consent.

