3.1. Primary Endpoint

- 1) The adenoma detection rate (ADR):

ADR was calculated by dividing the total number of patients being detected adenomas by the number of colonoscopies.

- 2) Cleanliness assessment of different intestinal segment in the artificial intelligence system
The artificial intelligence system evaluates the Boston Bowel Preparation score of the ascending colon, transverse colon and descending colon in real-time, and calculates the proportion of 1 Score

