3.2. Secondary Endpoints

- 1) The polyp detection rate (PDR): PDR was calculated by dividing the total number of patients being detected polyps by the number of colonoscopies.
- 2) The mean number of polyps per patient (MNP). MNP was calculated by dividing the total number of polyps by the number of colonoscopies.
- 3) The mean number of adenomas per patient (MAP). MAP was calculated by dividing the total number of adenomas by the number of colonoscopies.
- 4) PDR of different sizes. It was calculated by dividing the number of patients with polyps that large (≥ 10 mm), small (6-9 mm) and diminutive (≤ 5 mm) by the number of patients undergoing colonoscopy.
- 5) MNP of different sizes. It was calculated by dividing the number of polyps that large (≥ 10 mm), small (6-9 mm) and diminutive (≤ 5 mm) by the number of patients undergoing colonoscopy.
- 6) ADR of different sizes. It was calculated by dividing the number of patients with adenomas that large (≥ 10 mm), small (6-9 mm) and diminutive (≤ 5 mm) by the number of patients undergoing colonoscopy.
- 7) MAP of different sizes. It was calculated by dividing the number of adenomas that large (≥ 10 mm), small (6-9 mm) and diminutive (≤ 5 mm) by the number of patients undergoing colonoscopy.

- 8) ADR of different location. It was calculated by dividing the number of patients with adenomas detected in the rectum, sigmoid colon, descending colon, transverse colon, ascending colon, ileocecal region etc. by the Total number of patients undergoing colonoscopy.
- 9) MAP of different location. It was calculated by dividing the number of adenomas detected in the rectum, sigmoid colon, descending colon, transverse colon, ascending colon, ileocecal region etc. by the Total number of patients undergoing colonoscopy.
- 10) Scope-forward time. The time is taken to go from the the rectum to the ileocecal region.
- 11) Withdrawal time. The time is taken to finish the examination from the beginning of the ileocecal region.
- 12) Cecal intubation rate. It was calculated by dividing the number of colonoscopies that get to the ileocecal region by the total number of colonoscopies.
- 13) Boston Bowel Preparation Score of endoscopists. Endoscopists evaluate the different intestinal segment according Boston Bowel Preparation Scale(BBPS)

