4.1. Purpose

The purpose of this study is to develope the Endoangel with real-time intestinal cleanliness assessment. It can derive a decision curve for bowel cleanliness based on the relationship between the percentage of bowel segments with a Boston score of 1 and the detection rate of missed adenomas. To assist endoscopist in identifying patients who require a second colonoscopy, thus avoiding missed adenomas and excessive washing time costs due to subjective factors and poor decision-making. It can improve the quality of endoscopy and the detection rate of digestive tract lesions.

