7.3. Hypothetical test

The main assumptions are: There is a correlation curve between intestinal cleanliness score and the detection rate of adenoma. The use of EndoAngel can assess the intestinal cleanliness score in real time, and give a decision whether the patients need second colonoscopy

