7.4. Sample Size Calculation

The primary endpoint was the detection rate of Adenomas and the percentage of 1 score to get a correlation curve. In order to calculate the sample size more accurately, we prepare to collect 200 colonoscopies to explore the sample distribution, and then calculate the sample size according to the sample distribution.

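### Section 7.2 plans descriptive summaries only, so the plan contains no analysis that could yield the cleanliness–adenoma curve or the second-colonoscopy decision it promises

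*Combined protocol and SAP*

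**What the plan says.** **What is promised.** Section 4.1 (Purpose) describes a decision curve built on the "relationship between the percentage of bowel segments with a Boston score of 1 and the detection rate of missed adenomas". Section 7.3 states as its main assumption: "There is a correlation curve between intestinal cleanliness score and the detection rate of adenoma". It adds that EndoAngel will give a decision on whether a second colonoscopy is needed. Section 7.4 says the two primary endpoints serve to obtain this curve.

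**What is planned.** Section 7.2 has two sentences. The first reads "Continuous variables should be described by number of subjects, mean, standard deviation, median, minimum and maximum". The second gives frequency and percentage for categorical variables. Section 7.1 names the institution doing the analysis. Section 7.4 says "we prepare to collect 200 colonoscopies to explore the sample distribution, and then calculate the sample size according to the sample distribution". Section 7.5 defines the full analysis set (supportive) and the per-protocol set (main), with no model attached to either.

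**Design and schedule.** Section 4.2 describes a single-group, observational, single-centre study. The table in section 1.1 schedules colonoscopy on day 0 only.

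**Definitions the curve needs.**
- *Exposure.* The synopsis has EndoAngel work on edited patient video: it "evaluates the Boston Bowel Preparation Scale of the ascending colon, transverse colon and descending colon, and calculates the proportion of 1 Score". The Introduction and section 4.1 speak of a percentage of bowel segments.
- *Outcome.* The Introduction and section 4.1 refer to missed adenomas; sections 7.3 and 7.4 refer to adenoma detection.
- *Location.* In section 3.1 the system "evaluates the Boston Bowel Preparation score of the ascending colon, transverse colon and descending colon in real-time". The location-specific ADR in section 3.2 covers more of the bowel, "dividing the number of patients with adenomas detected in the rectum, sigmoid colon, descending colon, transverse colon, ascending colon, ileocecal region".

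**The concern.** A mean, a standard deviation and a percentage do not make a curve, and they do not lead to a decision rule. An analyst following section 7 literally would stop before the study question. Whoever goes further must choose the model, its shape, the adjustment and the cut-off after seeing the data.

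Two consequences follow. First, cleanliness is not assigned in this design. A raw curve could reflect who the patients are as well as how clean the bowel is. Second, a cut-off picked because it separates these patients best will look better in them than in anyone else. Since the intended use is a patient-level decision, both matter for what can be claimed.

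The later sample-size calculation is affected too. A size cannot be derived for a curve whose analysis is undefined.

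**Working it through.** **No stated figure to reproduce.** The 200 colonoscopies are an exploratory number. The plan gives no alpha, power, effect size or expected ADR. The core point is a reading of sections 7.1 to 7.5 against sections 4.1, 7.3 and 7.4, and needs no arithmetic. The figures below are conditional illustrations.

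**1. Cut-off search, continuous proportion (share of video).** Assumed: N = 200; ADR 25%; no true association; the cut is chosen for the largest z in the direction the Introduction implies (dirtier bowel, fewer adenomas); 20,000 runs per cell. For each cut,

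z = (p_clean − p_dirty) / √[p̄(1 − p̄)(1/n_clean + 1/n_dirty)], significant if z > 1.96.

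| Cuts searched | Nominally significant | Mean apparent gap (points) | Gap at ADR 15% to 35% |
|---|---|---|---|
| 1, pre-fixed at the median | 2.6% (theory 2.5%) | 0.0 | 0 |
| 4 | 7.8% | 5.0 | 4.2 to 5.6 |
| 9 | 12.8% | 8.1 | 6.7 to 8.9 |
| All, 10th to 90th percentile | 22.2% | 10.4 | 8.6 to 11.5 |

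At N = 800 the gaps for 4, 9 and all cuts fall to 2.5, 4.0 and 5.4 points, but the rates stay at about 8%, 13% and 24%. A larger sample does not remove the false positives. A cut-off locked in 200 patients and tested in 200 new ones gives 2.5% to 2.6% and a mean gap of 0.0.

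**2. The same search if the proportion is a share of three segments.** It then takes at most four values (0, 1/3, 2/3, 1). Assumed: each segment scores 1 with probability q, independently; cuts at ≥1, ≥2 and ≥3 segments; at least 5 patients per side; N = 200; ADR 25%.

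| q | Nominally significant | Mean apparent gap (points) |
|---|---|---|
| 10% | about 2% | 3.8 |
| 20% | about 4% | 3.8 |
| 30% | about 5% | about 5.7 |

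The false-positive rate is modest, but the apparent gap is about the size found for 4 cuts above.

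**3. Patients at the dirty end on that reading.** Under independence the expected number with all three segments at score 1 is 200q³: 0.2, 1.6 and 5.4 for q = 10%, 20% and 30%. With within-patient correlation ρ (beta-binomial, a = q(1 − ρ)/ρ, b = (1 − q)(1 − ρ)/ρ) it is 200·a(a+1)(a+2)/[(a+b)(a+b+1)(a+b+2)]. For ρ = 0.3 this gives 3.8, 10 and 19; for ρ = 0.5 it gives 7.7, 18 and 30. The documents give neither q nor ρ.

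**4. Feasibility of an adjusted model.** A linear term plus age and sex is 3 parameters; a three-knot spline makes it 4. At an assumed ADR of 25%, 200 × 0.25 = 50 events, so 50/3 = 16.7 or 50/4 = 12.5 events per parameter. Ten events for each of 4 parameters is 40 events, reached with 200 patients if ADR is at least 40/200 = 20%.

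**5. Size of a powered test in later patients.** Two-sided 5%, 80% power, share f above the cut-off:

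N = {1.96√[p̄(1 − p̄)(1/f + 1/(1 − f))] + 0.8416√[p₁(1 − p₁)/(1 − f) + p₂(1 − p₂)/f]}² / (p₁ − p₂)².

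For 25% v 15% and f = 0.5: (1.96 × 0.800 + 0.8416 × 0.7937)² / 0.01 = (2.236)² / 0.01 ≈ 500. For 18.75% v 11.25% the result is about 709, and for 12.5% v 7.5% about 1,128. All these rates are assumed.

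**The case against.** The strongest reply is that this is an exploratory study. Section 7.4 collects 200 colonoscopies to learn the distribution before sizing anything, and describing those data is a reasonable first step. That covers the sample size only. Section 7.3 states a hypothesis and a patient-level decision, section 7.4 ties the primary endpoint to the curve, and no later plan for the curve is mentioned.

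A second reply is that the simulation describes a search nobody has planned. This stands. A reader might infer that the sponsor will pick a cut-off and judge it in the same patients, so that the result will be inflated by 8 or 10 points. The documents do not say so; they are silent both ways. The simulated figures show what the silence permits.

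Four other inferences go too far:
- *Confounding has a known direction or size.* The documents give nothing from which to estimate either.
- *On the three-segment reading the problem vanishes.* The false-positive rate is low, but a gap of about 4 to 6 points remains.
- *On that reading the dirty end is almost empty.* That holds only if segments within a patient are independent, which no section supports.
- *Age and sex are not collected.* The CRF is not among the documents, and the schedule lists baseline characteristics.

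It is also fair that the sponsor defined ADR over any adenoma (section 3.1). The mismatch between scored segments and adenoma locations is a reason for a sensitivity analysis. It does not justify replacing the primary outcome.

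**Conclusion.** The point holds. Sections 7.1 to 7.5 contain no method that could produce the curve or the decision promised in sections 4.1, 7.3 and 7.4. This conclusion rests on the text alone.

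That an unadjusted curve is open to confounding follows from the design in section 4.2; no size or direction can be attached to it.

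The over-optimism is conditional on a cut-off being chosen and assessed in the same patients. With N = 200, ADR 25% and no true association, it amounts to about 8% to 22% nominally significant studies and gaps of about 5 to 10 points for a continuous proportion, against 2.5% and 0 for one pre-fixed cut. For a share of three independent segments (10% to 30% at score 1) it is about 2% to 5% and about 4 to 6 points. Patients with all three segments at score 1 could number anywhere from about 0.2 to 30 of 200, depending on assumed prevalence and within-patient correlation.

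**What to change.** 1. **Reconcile the definitions.** State whether the proportion of score 1 is a share of video (synopsis) or of segments (Introduction, section 4.1). Reconcile missed adenomas (Introduction, section 4.1) with adenoma detection (sections 7.3, 7.4): with a single colonoscopy day in the schedule, misses cannot be counted.

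2. **Add a primary analysis to section 7.2**, for example:

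> *Patient-level logistic regression of any adenoma detected (ADR as defined in 3.1) on the AI proportion of score 1, linear term, adjusted for age and sex. The curve is standardised to the age and sex distribution of the analysed patients and reported with 95% CI over the observed range. A three-knot restricted cubic spline is a sensitivity analysis if the proportion is a share of video, the knots are distinct and there are at least 40 events. Detection limited to the AI-scored segments is a sensitivity analysis.*

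   Confirm that age and sex are among the baseline characteristics recorded (section 1.1).

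3. **Pre-state the statistical criterion for any cut-off.** If patients are enrolled after the first 200, lock the cut-off in the first 200 and assess it once in the later patients, with estimate and 95% CI. Otherwise report optimism-corrected performance and label the cut-off exploratory. The correction is partial: in a null simulation (400 runs, 100 resamples each), bootstrap reduced apparent gaps of 5.1, 8.4 and 9.7 points (4, 9 and all cuts) to 1.7, 2.8 and 3.0, not to 0. The clinical rule itself remains the sponsor's.

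4. **Report how many patients were excluded or withdrawn for poor preparation** (section 2.2, criterion 12; section 5.4.2). Adjustment cannot restore that end of the curve.

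**Cost.** SAP text, modest analysis work, and a less favourable or less precise estimate of cut-off performance. A formally powered test in later patients is optional and could be large: about 500, 709 or 1,128 patients under the three pairs of assumed rates above, with half above the cut-off.

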7.3. Hypothetical test

The main assumptions are: There is a correlation curve between intestinal cleanliness score and the detection rate of adenoma. The use of EndoAngel can assess the intestinal cleanliness score in real time, and give a decision whether the patients need second colonoscopy

7.4. Sample Size Calculation

The primary endpoint was the detection rate of Adenomas and the percentage of 1 score to get a correlation curve. In order to calculate the sample size more accurately, we prepare to collect 200 colonoscopies to explore the sample distribution, and then calculate the sample size according to the sample distribution.

7.5. Statistical analysis set

All patients who met the inclusion and exclusion criteria were considered eligible for recruitment.

The two analysis sets in this study are defined as follows:

- The full analysis set (FAS) population analysis set will contain all eligible cases and shedding cases, but does not include culling cases.
- The Compliance (PP) population analysis set will include all subjects in the FAS analysis set with no significant deviation from the program.

Intention-to-treat and conformity analysis sets should be used to analyze the primary efficacy endpoints. The main analysis will be based on the PP analysis set. FAS analysis was regarded as supportive analysis.

8. Device Description

EndoAngel

Version: EA 2301

9. Abbreviations

Abbreviations	Full Name	Chinese
AE	Adverse Event	不良事件
CFDA	China Food and Drug Administration	国家食品药品监督管理总局
CNDA	China National Drug Administration	国家食品药品监督管理总局
CRF	Clinical Record File	病例报告表
CTCAE	Common Terminology Criteria for Adverse Events	不良事件常规评价标准
EC	Ethical Committee	伦理委员会
ICD	Informed Consent Document	知情同意文件
ICF	Informed Consent Form	知情同意书
ITT	Intention to Treat	意向治疗分析集
PP	Per Protocol	符合方案集
SAE	Serious Adverse Event	严重不良事件
CRC	Colorectal cancer	结肠癌
MNP	the Mean Number of Polyps per Procedure	平均每例肠镜发现的息肉个数
MAP	the Mean Number of Adenomas per Procedure	平均每例肠镜发现的腺瘤个数
PDR	Polyp Detection Rate	息肉发现率
ADR	Adenoma Detection Rate	腺瘤检出率
BBPS	Boston Bowel Preparation Scale	波士顿肠道评分量表

10. References

- 1 Hosokawa,O. et al. Difference in accuracy between gastroscopy and colonoscopy for detection of cancer. *Hepatogastroenterology* 2007;54:442-4.
- 2 Bisschops,R. et al. Performance measures for upper gastrointestinal endoscopy: a European Society of Gastrointestinal Endoscopy (ESGE) Quality Improvement Initiative. *Endoscopy* 2016;48:843-64.
- 3 Rutter,MD. et al. Quality in gastrointestinal endoscopy. *Endoscopy* 2014;46:526-8.
- 4 Gado,AS. et.al. Quality assurance in gastrointestinal endoscopy: An Egyptian experience. *Arab journal of gastroenterology : the official publication of the Pan-Arab Association of Gastroenterology* 2016;17:153-8.
- 5 Faigel DO. Quality, competency and endosonography. *Endoscopy* 2006;38 Suppl 1:S65-9.
- 6 Malheiro,R. et al. Methodological quality of guidelines in gastroenterology. *Endoscopy* 2014;46:513-25.
- 7 Chokshi, RV. et al. Prevalence of missed adenomas in patients with inadequate bowel preparation on screening colonoscopy. *Gastrointest Endosc*, 2012. 75(6): p. 1197-203.

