5.2.2. Patient Selection

All patients who underwent colonoscopy, agreed to use EndoAngel and generally meet the study requirements were screened based on the inclusion/exclusion criteria. Patients who passed the screening were enrolled and recorded in the subject screening and enrollment tables. There is no bias in the choice of the enrolled subjects. The date of screening, the results (enrolled or not), and the primary reason for not selecting subjects (such as not meeting inclusion criteria, or not interested in participating in the study) will be recorded.

After the patients are enrolled, the research center should complete the preoperative study data collection.

It is desirable to be able to collect complete data for all enrolled patients, without those withdrawal from the study.

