5.3.5. Specimen handling procedure

5.4. Suspension and withdrawal

Patients who were screened and confirmed to be eligible for the study, signed the informed

consent and completed the randomization were considered as enrolled. If serious program deviation, withdrawal, or death occurs, the subject study is considered to be suspended. If the subject discontinues the study after obtaining informed consent, the data before the discontinuation will still be included in the study-related analysis.

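### The main analysis uses a per-protocol set with undefined removal rules, so the primary ADR and the cleanliness–ADR curve can be selected on findings or on cleanliness

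*Combined protocol and SAP*

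**What the plan says.** All references are to the combined protocol and SAP.

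- **Section 7.5 (analysis sets).** The FAS "will contain all eligible cases and shedding cases, but does not include culling cases". The PP set "will include all subjects in the FAS analysis set with no significant deviation from the program". Then: "The main analysis will be based on the PP analysis set", with the FAS as supportive. The section also calls for an intention-to-treat set, which is not one of the two sets it defines. Culling, shedding and significant deviation are not defined. No one is named to decide them and no time is set.
- **Section 2 (Patient Selection).** "Patients who met all criteria and signed informed consent may be excluded from the study due to" two reasons. One is withdrawn consent. The other is "Endoscopists' professional advices/medical reasons (only under very limited conditions to avoid researcher bias"). The conditions are not listed and no time limit is given.
- **Section 5.4.** "If the subject discontinues the study after obtaining informed consent, the data before the discontinuation will still be included in the study-related analysis".
- **Section 5.4.2.** Withdrawal during the procedure is listed for perforation, bleeding, allergy to narcotic drugs, poor intestinal cleanliness, and inability to complete because of obstruction or other reasons.
- **Section 5.2.2.** "It is desirable to be able to collect complete data for all enrolled patients, without those withdrawal from the study".
- **Sections 3.1 and 7.4.** ADR is a primary endpoint and is plotted against the proportion of score 1 to give the correlation curve. Its denominator is the number of colonoscopies, with no analysis set named.

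**The concern.** This is a single-group observational study. No assigned treatment is compared, so the usual reason for a PP analysis, estimating the effect of a treatment taken as planned, does not apply. What a PP set does here is select patients partly by events during or after the colonoscopy.

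Some of those events may be related to the two quantities on the curve. Bleeding, perforation and obstruction can accompany a lesion, a biopsy or a polypectomy. Poor cleanliness is the exposure itself. Discretionary exclusion under section 2 is not confined to the time before the endoscopist has seen the bowel. With the removal terms undefined, two analysts could follow the text and report different primary ADRs from the same patients. The curve could also be thinnest where the second-colonoscopy decision is to be made.

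**Working it through.** The plan gives no expected ADR, dropout rate, alpha or power, so there is no figure of its own to reproduce. The check has a textual part and an illustration on assumed rates.

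**1. Can a withdrawn patient leave the main analysis?**
- Section 5.4 keeps data up to discontinuation in the study-related analysis, but does not say in which set.
- The FAS keeps shedding cases. If these are dropouts, that agrees with 5.4. The FAS also loses culling cases, and nothing separates the two.
- The PP set loses significant deviations. Section 5.4 groups serious deviation and withdrawal together as suspending the subject, but does not call every withdrawal a deviation.
- So removal is possible and is neither required nor prevented.

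**2. Which routes are tied to outcome or exposure?**
- Tied to lesions: bleeding, perforation and obstruction in 5.4.2. In addition, 5.3.4 asks for follow-up to treatment within 7 days only where lesions were found and not biopsied, so only those patients can breach that duty.
- Tied to cleanliness: the 5.4.2 trigger, and exclusion criterion 12 (poor preparation with failure to reach the cecum), which can only be judged at colonoscopy.
- Discretionary: section 2, with no time limit.

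**3. Size for ADR, all rates assumed.**

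Differential loss: retained ADR = a(1 − w1) / [a(1 − w1) + (1 − a)(1 − w0)], where a is the true ADR and w1 and w0 are the shares of adenoma and adenoma-free patients lost. With a = 0.30:
- w1 = 0.05, w0 = 0.01: 0.285 / (0.285 + 0.693) = 29.1%, a shift of −0.9 points.
- w1 = 0.10, w0 = 0.02: 0.270 / (0.270 + 0.686) = 28.2%, a shift of −1.8 points.

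Loss of adenoma-free patients only, starting from an assumed 50/200 = 25.0%:
- 10 removed: 50/190 = 26.3%, +1.3 points.
- 20 removed: 50/180 = 27.8%, +2.8 points.

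Range, using PP ADR = (X − x)/(N − k), with N = 200 (section 7.4), X = 60 adenoma patients (30%), k removed, and x of those with an adenoma. For k = 20:
- none has an adenoma: 60/180 = 33.3%
- removal unrelated to adenoma: 54/180 = 30.0%
- twice the average adenoma rate: 48/180 = 26.7%
- all have an adenoma: 40/180 = 22.2%

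The two extremes are 50/190 = 26.3% and 60/190 = 31.6% for k = 10, and 20/160 = 12.5% and 60/160 = 37.5% for k = 40. For comparison, the 95% half-width at N = 200 and 30% is 1.96 × √(0.3 × 0.7 / 200) = 6.4 points.

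**4. Effect on the curve, assumed.** Let the proportion of score 1 be uniform on 0 to 1 and let ADR fall linearly from 35% to 15%. The mean ADR is 25%. Removing the dirtiest 10% gives 0.35 − 0.20 × 0.45 = 26.0%, and removing the dirtiest 20% gives 0.35 − 0.20 × 0.40 = 27.0%. In simulation the correlation weakens from −0.134 to −0.120 and −0.105. Under a correct linear model, removal on cleanliness alone would not bias the slope. It does remove the observations at the low-cleanliness end, so the curve there rests on extrapolation.

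**The case against.** Several stronger readings are tempting, and the documents do not support them.

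- *Section 2 deletes the data of these patients and so contradicts 5.4.* Section 2 says such patients may be excluded from the study, which concerns participation. Stopping participation while keeping earlier data is coherent and fits an FAS that keeps dropouts. Section 5.2.2 is a wish about data collection, not an analysis rule. It does not follow that the text contains three rules giving three ADRs; it defines two analysis sets. What stands is that the sections should state one rule.
- *The 5.4.2 withdrawals are PP exclusions.* No passage says so. They can become so only because the term is undefined.
- *Endoscopists may freely remove patients once results are known.* Section 2 limits this ground to very limited conditions, expressly to avoid researcher bias. Section 5.4.1 describes withdrawal before the procedure and 5.4.2 withdrawal during it. During the procedure the endoscopist sees lesions, not histology. Removing 10 or 20 of 200 in this way would sit badly with that wording, so those figures show sensitivity and are not a forecast. The missing time limit stands.
- *A PP set has no purpose here.* It has some. The synopsis requires the endoscopist not to withdraw the scope while flushing, and irrigation, biopsy and polyp-observation clips are cut from the video. Breaches can distort the AI score. That justifies PP as a sensitivity analysis, but not as the main estimate of ADR.

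It is also fair to say that gastrointestinal bleeding, obstruction and perforation are already entry exclusions, that no event rates are given, and that both sets are to be analysed for the primary endpoints, so a gap between them would be visible. The FAS is only a partial safeguard, because it too loses undefined culling cases.

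**Conclusion.** The concern holds as a gap in the rules. The main analysis rests on a set whose membership depends on undefined terms, with no requirement that membership be settled before findings or pathology are known. Several routes that could lead out of that set are linked to lesions or to cleanliness. The text does not show that any patient will be removed in this way.

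Neither direction nor size can be determined from the documents. Loss of patients with lesions lowers ADR; loss of adenoma-free or poorly prepared patients would raise it, if poor preparation goes with fewer detected adenomas. Moderate assumed rates give shifts of about 1 to 3 points, and 3.3 points when 20 of 200 are removed with twice the average adenoma rate at an ADR of 30%. If removal is unrelated to adenoma, the shift is zero. These moderate shifts are smaller than the sampling error at 200 colonoscopies, but they are systematic and would not shrink with a larger final sample. The possible loss of the low-cleanliness end may matter more, since the curve is meant to support decisions there. This should be corrected, because the remedy is cheap.

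**What to change.** 1. **Main ADR analysis (7.5):** all consented patients who met the criteria assessable before the procedure and had the colonoscope inserted, with all data collected up to discontinuation, including pathology of specimens already taken. Use PP as the sensitivity analysis. The present FAS does not deliver this set, because it drops culling cases.
2. **Curve:** all such patients with at least one evaluable segment. Report the number and the ADR of those without usable video.
3. **Section 2:** allow discretionary exclusion from the analysis only before scope insertion. This concerns the analysis and leaves decisions about the patient's care untouched.
4. **Definitions (7.5):** define culling and significant deviation by criteria independent of findings and of cleanliness. Classify deviations before pathology is known, and report each exclusion with its reason and timing.
5. **Withdrawn patients:** reconcile sections 2, 5.4 and 7.5 to one rule on their data.

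The cost is wording in sections 2, 5.4 and 7.5, with no new patients. The small downside is that the main set will contain some incomplete examinations and some procedural breaches, which the PP sensitivity analysis addresses.
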